3.12.1 PRO Endpoints

Exploratory PRO endpoints include mean score changes from baseline to the latest time point, where the completion rate and compliance rates are still high enough (e.g. close to 60 and 80%, respectively) based on blinded data review, as measured by:

- EORTC QLQ-C30 global health status/quality of life scale
- All EORTC QLQ-C30 sub-scales/items
- EQ-5D VAS

The other PRO endpoints are:

- The time to deterioration (TTD) for the QLQ-C30 global health status/quality of life scale.
- The number and proportions of deterioration/stable/improvement from baseline to the latest time point, where the completion rate and compliance rates are still high enough (e.g. close to 60 and 80%, respectively) for all QLQ-C30 sub-scales/items.

3.12.2 Scoring Algorithm

The QLQ-C30 includes five functional dimensions (physical, role, emotional, cognitive, and social), three symptom scales (fatigue, nausea/vomiting, and pain), and six single item measures (dyspnea, sleep disturbance, appetite loss, constipation, diarrhea, and financial difficulties).

QLQ-C30 Scoring: For each scale or item, a linear transformation will be applied to standardize the score as between 0 and 100, according to the corresponding scoring standard. For functioning and global health status/quality-of-life scales, a higher value indicates a better level of function; for symptom scales and items, a higher value indicates increased severity of symptoms.

According to the QLQ-C30 Manuals [12], if items $I_1, I_2, ..., I_n$ are included in a scale, the linear transformation procedure is as follows:

PAGE 27

- 1. Compute the raw score: $RS = (I_1 + I_2 + ... + I_n)/n$
- 2. Linear transformation to obtain the score *S*:

Function scales:
$$S = \left(1 - \frac{RS - 1}{Range}\right) \times 100$$

Symptom scales/items: $S = \frac{RS - 1}{Range} \times 100$
Global health status/QoL: $S = \frac{RS - 1}{Range} \times 100$

Range is the difference between the maximum possible value of RS and the minimum possible value. If more than half of the items within one scale are missing, then the scale is considered missing, otherwise, the score will be calculated as the average score of those available items.

3.12.3 The Schedule for PRO Data Collection

Table 10 provides the schedule for PRO data collection.

Week	Cycle	MK-3475	Placebo
Week 0	C1	✓	✓
Week 3	C2	✓	✓
Week 6	C3	✓	✓
Week 9	C4	✓	✓
Week 12	C5	✓	✓
Week 18	C7	✓	✓
Week 27	>=C8	✓	✓
Week 36	>=C8	✓	✓
Week 45	>=C8	✓	✓
End of Treatment		✓	✓
30-day Safety follow-up		✓	✓

Table 10PRO Data Collection Schedule

All PROs are to be performed at Cycle 1, Cycle 2, Cycle 3, Cycle 4, Cycle 5, and Cycle 7 before dosing. After Cycle 7 (Week 18), PROs are to be performed every 9 weeks (e.g., Week 27, Week 36, Week 45). PROs are to be performed up to a year or End of Treatment, whichever comes first, at treatment discontinuation, and at the 30-day post-treatment discontinuation follow-up visit.

The general rule of mapping relative day to analysis visit is provided in Table 11. The relative days are counted from the date the first dose.

Week	Day	Day Range
Week 0	1	-7 - 1
Week 3	21	2 - 31
Week 6	42	32 - 52
Week 9	63	53 - 73
Week 12	84	74 - 105
Week 18	126	106 - 157
Week 27	189	158 - 220
Week 36	252	221 - 283
Week 45	315	284 - 346

Table 11Mapping Relative Day to Analysis Visit

At each scheduled visit, two instruments, EORTC QLQ-C30 and EQ-5D-3L, will be collected. If a patient does not complete the PRO instruments, the site staff will record the reason for missingness from pre-defined choices by using a miss-mode form. If there are multiple PRO collections within any of the stated time windows, we use the closest collection to the target day.

3.12.4 Analysis Populations

MK-3475

SUPPLEMENTAL SAP

The PRO analyses are based on the PRO Full Analysis Set (FAS) population, defined as all randomized participants who have at least one PRO assessment available and have received at least one dose of the study intervention. This population consists of all randomized patients who have received at least one dose of study medication and have completed at least one PRO assessment.

3.12.5 Statistical Methods

3.12.5.1 PRO Compliance Summary

Completion and compliance of EORTC QLQ-C30 and EQ-5D3L by visit and by treatment will be described based on PRO FAS population. Numbers and percentages of complete and missing data at each visit will be summarized for each of the treatment groups. An instrument is considered complete if at least one valid score is available according to the missing item rules outlined in the scoring manual for the instrument.

Completion rate in the FAS population is defined as the percentage of number of subjects who complete at least one item over the number of subjects in the PRO FAS population at each time points.

 $Completion Rate = \frac{Number of subjects who complete at least one item}{Number of subject s in PRO FAS popula tion}$

The completion rate is expected to shrink in the later visits during study period due to the subjects who discontinued early. Therefore, another measurement, compliance rate of eligible subjects will also be employed as the support for completion rate. Compliance rate is defined as the percentage of number of subjects who complete at least one item over number of eligible subjects who are expected to complete the PRO assessment (not including the subjects missing by design (such as death, discontinuation, translation not available)).

Compliance Rate = $\frac{Number of subjects who complete at least one item}{Number of eligible subjects who are expected to complete}$

The reasons for non-completion and non-compliance will be summarized.

In addition, reasons for non-completion as scheduled of these measures will be collected using miss-mode forms filled by site personnel and will be summarized in table format. The schedule (study visits and estimated study times) and mapping of study visit to analysis visit for PRO data collection is provided in the Table 10 and Table 11.

3.12.5.2 Mean Change from Baseline

The time point for the mean change from baseline is defined as the latest time point at which completion rate $\geq 60\%$ and compliance rate $\geq 80\%$ based on blinded data review prior to the database lock for any PRO analysis. The primary time point for the analyses of PRO endpoint is Week 12.

To assess the treatment effects based on the PRO score change from baseline, for each continuous endpoint defined, a constrained longitudinal data analysis (cLDA) model proposed by Liang and Zeger [8] will be used. This model assumes a common mean across treatment groups at baseline and a different mean for each treatment at each of the post-baseline time points. In this model, the response vector consists of the baseline value and the values observed at each post-baseline time point. Time is treated as a categorical variable so that no restriction is imposed on the trajectory of the means over time. The analysis model will include the PRO score as the response variable, and treatment by study visit interaction, and stratification factors used for analyses of the primary endpoints as covariates.

The cLDA model is specified as follows:

$$E(Y_{ijt}) = \gamma_0 + \gamma_{jt}I(t > 0) + \beta X_{i}, j = 1, 2, 3, ..., n; t = 0, 1, 2, ..., k$$

Where Y_{ijt} is the PRO score for subject *i*, with treatment assignment *j* at visit *t*, γ_0 is the baseline mean for both treatment groups, γ_{jt} is the mean change from baseline for treatment group *j* at time *t*, X_i is the stratification factor vector for this patient, and β is the coefficient vector for stratification factors. An unstructured covariance matrix will be used to model the correlation among repeated measurements. The cLDA model implicitly treats missing data as missing at random (MAR).

The treatment difference in terms of least square (LS) mean score change from baseline to the time point as specified at the beginning of this section will be estimated from this model, together with 95% CI and nominal p-value. In addition, model-based LS mean score with 95% CI will be provided by treatment group and study visit.

If the unstructured covariance model fails to converge with the default algorithm, then Fisher scoring algorithm or other appropriate methods can be used to provide initial values of the covariance parameters. In the rare event that none of the above methods yield convergence, a structured covariance such as Toeplitz can be used to model the correlation among repeated measurements. In this case, the empirical option for PROC MIXED in SAS 9.4 will be used because the sandwich variance estimator is asymptotically unbiased.

3.12.5.3 Time to Deterioration

Time to deterioration (TTD): For the EORTC QLQ-C30, a 10 points or greater worsening from baseline for each scale represents a clinically relevant deterioration based on prior literature [9] [10] [11] TTD is defined as the time to first onset of 10 or more (out of 100) deterioration from baseline in a given scale/sub-scale/item and confirmed by a second adjacent 10 or more deterioration from baseline.

The Kaplan-Meier method will be used to estimate the TTD curve for each treatment group. The estimate of median time to deterioration and its 95% confidence interval will be obtained from the Kaplan-Meier estimates. The treatment difference in TTD will be assessed by the stratified log-rank test. A stratified Cox proportional hazard model with Efron's method of tie handling and with a single treatment covariate will be used to assess the magnitude of the treatment difference (i.e., hazard ratio). The hazard ratio and its 95% CI will be reported. The stratification factors used for analyses of the primary endpoints will be used as the stratification factors in both the stratified log-rank test and the stratified Cox model.

The approach for the time-to-deterioration analysis will be based on the assumption of noninformative censoring. The participants who do not have deterioration on the last date of evaluation will be censored. **Table 12** provides censoring rule for TTD analysis.

Scenario	Outcome
Deterioration documented	Event observed at time of assessment (first deterioration)
Ongoing or discontinued from study without deterioration	Right censored at time of last assessment
No baseline assessments	Right censored at treatment start date

Table 12Censoring Rules for Time-to-Deterioration

3.12.5.4 Proportions of Deterioration/Stable/Improvement

Patients' post-baseline PRO score will be classified as "improved", "stable" or "deteriorated" according to a 10 points or greater change for each of the instrument/scale, as this magnitude of change is perceived by patients as being clinically significant.

Since missing data cannot be ignored at the time point as specified at the beginning of Section 3.12.5.2, the number and proportion of patients who "improved", "stable", or "deteriorated", from baseline will be summarized by treatment group and at the prior analysis visit based on MAR imputation of missing data.

4 **REFERENCES**

- 5. Uno, H., et al. Moving Beyond the Hazard Ratio in Quantifying the Between-Group Difference in Survival Analysis. J Clin Oncol. 2014;32 (22):2380-2385.
- 11. King M.T. The interpretation of scores from the EORTC quality of life questionnaire QLQ-C30. Qual Life Res 5:555-567, 1996

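### The improved/stable/deteriorated PRO proportions use MAR imputation with no exception for death, so some subjects who died before the visit may be reported as improved or stable.

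*SAP*

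**What the plan says.** SAP 3.12.5.4 puts each post-baseline QLQ-C30 score into one of three categories, using a 10-point change from baseline. It gives its reason for imputing: "Since missing data cannot be ignored at the time point as specified at the beginning of Section 3.12.5.2". The counts and proportions are then summarized by treatment group, "at the prior analysis visit based on MAR imputation of missing data". No imputation model is named, and death is not mentioned.

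Three other places in the PRO section bear on this:

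- **Population (SAP 3.12.4).** The set is "all randomized participants who have at least one PRO assessment available and have received at least one dose of the study intervention". Being alive at the visit is not required.
- **Compliance (SAP 3.12.5.1).** Here the PRO section does name death. The compliance denominator counts subjects expected to complete the assessment, "not including the subjects missing by design (such as death, discontinuation, translation not available". That carve-out serves the compliance rate and is not repeated in 3.12.5.4.
- **Time point (SAP 3.12.5.2).** It is the latest visit with completion of at least 60% and compliance of at least 80% on blinded review, followed by the statement "The primary time point for the analyses of PRO endpoint is Week 12". SAP 3.12.1 words the thresholds more loosely: "e.g. close to 60 and 80%, respectively".

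**The concern.** A subject who has died has no quality-of-life score at the visit, so nothing exists for imputation to recover. An imputed value describes a hypothetical state, and once it is cut at 10 points the table presents that state as an observed patient category. A reader who sees a percentage of patients improved or stable at Week 12 would assume those patients were alive at Week 12.

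The group is not small in second-line advanced HCC, and its size is expected to differ between arms, because a survival difference is the trial's primary hypothesis. The SAP is explicit about death or missing data elsewhere: death is an event for PFS, is censored for TTP (Table 2), and missing data count as non-response for ORR (Table 4). The PRO proportions have no comparable rule for death.

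**Working it through.** The SAP gives no figure for the PRO proportions. The only planning figures to borrow are those for OS, so those are checked first.

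**1. Do the OS inputs reproduce the plan's power?** Inputs from SAP 3.8: 345 events, hazard ratio 0.7, one-sided alpha 2.3%, 2:1 allocation. By the Schoenfeld formula:

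- sqrt(345 × 2/3 × 1/3) × |ln 0.7| = 8.756 × 0.3567 = 3.123
- 3.123 − 1.995 = 1.128, which gives power 0.870

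The plan states about 87%, so the inputs are read correctly.

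**2. Deaths by Week 12.** Week 12 is Day 84 (SAP Table 11), so t = 84 / 30.4375 = 2.76 months. Survival is exponential with a control median of 6.0 months (SAP 3.8), and 450 subjects at 2:1 are 300 and 150.

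- Control: 1 − exp(−ln 2 × 2.76 / 6.0) = 27.3%, about 41 of 150
- Pembrolizumab: 1 − exp(−0.7 × ln 2 × 2.76 / 6.0) = 20.0%, about 60 of 300
- Total: about 101 of 450, or 22%

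If the blinded review selected Week 18 (Day 126) instead, the same formula gives about 142 deaths.

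**3. Does the time-point rule keep this group small?** Completion and compliance share a numerator, so eligible subjects as a fraction of the PRO set equal completion divided by compliance. With both exactly at threshold this is 0.60 / 0.80 = 75%. The rule therefore tolerates 25% of the set falling in the excluded group, which takes in death, discontinuation and unavailable translation. A death share of 20% to 27% is of the same order, so the rule does not remove the problem.

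**4. Where would the imputed subjects fall?** Let q be the share of imputed values for the dead that land in improved or stable. The documents give no q. The range below is an assumption, taken equal in both arms.

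| q (assumed) | Improved or stable, of about 101 | Deteriorated |
|---|---|---|
| 0.3 | 30 | 71 |
| 0.6 | 61 | 40 |
| 0.8 | 81 | 20 |

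**The case against.** The strongest reply is that the SAP is silent rather than wrong. It never says that the dead are imputed, and 3.12.5.1 shows that it can separate death from ordinary missingness. This stands in part: the authors may have intended to leave the dead out. But the rule in 3.12.5.4 covers missing data without qualification, the population includes the dead, and 3.12.5.1 itself files death as a kind of missingness. Following the text as written imputes them.

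A reader might infer more: that the dead are all counted as improved or stable. The documents do not support this. Imputation can equally place a subject in deteriorated. A model that conditions on the subject's own earlier scores would tend to give declining values to someone who declined before death, so the rate among scored survivors cannot simply be applied to the dead. With the model unstated, q cannot be derived.

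A reader might also infer that the survival difference distorts the comparison between arms. That does not follow. If q and the share among scored subjects are both 0.6 in each arm, the imputed proportions are 60% and 60%. Taking the dead out of the numerator gives 0.6 × (1 − 0.273) = 44% for control and 0.6 × (1 − 0.200) = 48% for pembrolizumab. The 4-point gap is the assumed OS effect entering the table. It reflects a change of estimand, not a bias removed. Moreover, 3.12.5.4 specifies a summary by arm and no between-arm test.

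The death rates can also be challenged. Protocol 5.1.2 requires Child-Pugh A, ECOG 0 or 1 and a predicted life expectancy above 3 months. Week 12 falls before 3 months, so a constant hazard may overstate early deaths. The PRO set also differs from the ITT population to which the planning assumptions apply. Both caveats stand.

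**Conclusion.** The concern holds in a limited form. As written, SAP 3.12.5.4 assigns imputed quality-of-life categories to subjects who died before the visit, and some of them may be reported as improved or stable. The resulting proportions cannot be read as the state of patients at that visit.

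The affected group is about 22% of subjects at Week 12 under exponential survival, the OS planning values and ITT numbers, and possibly fewer given the entry criteria. The split across categories is not determinable from the documents. The 30 to 81 range shows only how far it depends on the assumed q.

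The consequence is modest. SAP 3.12 makes the PRO endpoints exploratory, without formal hypotheses or multiplicity adjustment, and nothing confirmatory depends on this table.

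**What to change.** In SAP 3.12.5.4:

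- apply MAR imputation only to subjects alive at the analysis visit, and name the imputation model;
- show death before the visit as a fourth category, by arm, with the PRO full analysis set as denominator;
- align the wording with 3.12.5.1, so that death is treated as its own state and not as missing data to be filled in.

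Counting death as deteriorated, or using a while-alive denominator, would also be defensible if stated. The separate category is preferable because it keeps the survival difference visible and lets a reader recover either alternative.

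No new data are needed, since survival status is already collected (Protocol 6.1 and 7.1.6.3.4). The cost is one derived category and a few lines of SAP text. The reported improved and stable percentages will be lower, and a difference between arms may appear that is due to survival, so the table should carry a note saying so.
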